14.5 Descriptive Statistics

Summaries of the characteristics of the patients in each treatment arm at baseline will be prepared for both the intent-to-treat and evaluable populations. The summary will minimally include: gender distribution, age, years of use, route of administration, ethnic distribution, education, income, and ASI composite scores. Another summary will be prepared to show dropouts/retention over time in each treatment group and for major subgroups. The number of missing observations will be compared between treatment arms and for major subgroups. The compliance of each group at each assessment day will be summarized.

All adverse events will be reported in tabular form indicating the frequency of each type of event by various demographic characteristics such as gender, ethnicity, age, duration

of addiction, other medical problems both related to and independent of the addiction, and combinations of these characteristics.

14.6 Sample Size Estimate

Sample size and power calculations were made based on the primary outcome measure, treatment response. It was assumed that there would be 20% (maximally) treatment responders in the clonidine group and 30% treatment responders in the BUP/NX group. Using a Chi-Square test power analysis, and assuming a 2:1 buprenorphine:clonidine randomization ratio, an N of 360 is sufficient to detect the 10% difference in number of responders in the two arms with an alpha of 0.05 and a power of 90%. Therefore, the number of patients in the BUP/NX arm is proposed to be 240 and the number in the clonidine arm is to be 120.

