14.4 Analysis Plan

Baseline characteristics of groups will be generated using demographic data from intake questionnaires as well as the Addiction Severity Index. Information summarized will include gender distribution, age, years of use, route of administration, ethnic distribution, education, income, and ASI composite scores. Appropriate 2-sided *t*-tests or chi-square tests will be used to test for equivalence between groups. Inequalities between groups at baseline will be used as cofactors in analyses of outcome variables if related to outcomes.

Each of the primary and other primary outcome measures will be analyzed for the intent-to-treat population. The primary outcome measure is based on an intent-to-treat principle, and therefore cannot be analyzed in the evaluable population. The other primary outcome measures, however, will be analyzed for the evaluable population in addition to the intent-to-treat population. By examining the other primary outcome measures for the evaluable population, the long-term efficacy in treatment responders can be explored. Comparing results from the intent-to-treat and evaluable population analyses will also provide estimates of the effect of missing data. Major differences in the results, if any, will be further explored. While there is every intent to be complete in describing the analyses to be performed, it is not possible to anticipate every contingency, and some adjustments may be required to meet constraints posed by the structure of the data.

The primary outcome measure, treatment responders, will be compared between groups using the Chi-square statistic. Two-group two-tailed t-tests and analysis of variance (with repeated measures where appropriate) will be used to evaluate group differences in other primary outcomes, including retention, number of negative urines and number of consecutive negative urines, and frequency of ancillary medications dispensed. Survival analysis techniques including log- rank statistics will be used to evaluate treatment response over the duration of treatment and follow-up. Both retention in treatment and retention in treatment with negative urine tests for opiates will be evaluated. Repeated measures such as the ASI, VAS, COWS, ARSW will be evaluated using an appropriate repeated measures test such as generalized estimating equations.

Statistical tests will be two-sided, with alpha set at 0.05. Confidence intervals will be two-sided with a 95% confidence coefficient.

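### The stated 90% power is wrong: 240 vs 120 patients give about 53% power for 30% vs 20% responders

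*Protocol*

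**What the plan says.** Section 14.6 bases the sample size on the primary outcome, treatment response. It assumes that "there would be 20% (maximally) treatment responders in the clonidine group and 30% treatment responders in the BUP/NX group", uses a chi-square power analysis, and states, "assuming a 2:1 buprenorphine:clonidine randomization ratio, an N of 360", that this number is "sufficient to detect the 10% difference in number of responders in the two arms with an alpha of 0.05 and a power of 90" per cent. From this it concludes that "the number of patients in the BUP/NX arm is proposed to be 240 and the number in the clonidine arm is to be 120".

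Three other places fix the rest of the calculation:

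- Section 14.4 names the chi-square statistic for the primary comparison and adds: "Statistical tests will be two-sided, with alpha set at 0.05".
- Section 14.2.1 takes all randomized patients as the denominator.
- Section 14.1 counts a patient who does not attend or gives no urine sample as a non-responder, so dropout does not reduce the analysed number.

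**The concern.** The protocol prints every input to the power calculation, so the figure can be checked without assumptions, and it looks far too high. As a rule of thumb, 90% power at two-sided 0.05 needs a true difference of about 3.24 standard errors (1.96 + 1.28). With 240 and 120 patients and rates near 25%, the standard error of the difference is close to 5 points, so 10 points is only about two standard errors. That puts power near one half.

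Power for the primary outcome is the only reason section 14.6 gives for the size of the trial. Anyone relying on it would believe that a real 10-point benefit is missed 10% of the time. If the true figure is near 47%, a non-significant result could be taken as good evidence against such a benefit when it is not. Section 13.5 plans no interim efficacy analysis by arm, and the protocol describes no re-estimation of the sample size, so nothing in it would correct the shortfall during the trial.

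**Working it through.** **Inputs, all from the protocol.** p_C = 0.20, p_B = 0.30, n_C = 120, n_B = 240, chi-square test, alpha 0.05 (section 14.6); two-sided (section 14.4); all 360 randomized patients analysed (sections 14.1 and 14.2.1).

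**Attempt to reproduce the stated 90%.** For two proportions the Pearson chi-square test is the square of the pooled z test, so

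power = Φ[(p_B − p_C − 1.96 × SE0) / SE1]

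- Pooled rate: (120 × 0.20 + 240 × 0.30) / 360 = 96/360 = 0.2667.
- SE0 (no difference) = √[0.2667 × 0.7333 × (1/120 + 1/240)] = 0.04944.
- SE1 (assumed rates) = √[0.20 × 0.80/120 + 0.30 × 0.70/240] = 0.04699.
- (0.10 − 1.96 × 0.04944) / 0.04699 = 0.066, and Φ(0.066) = **0.526**.

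Exact enumeration over both binomial distributions gives 53.3% for the Pearson test and 47.6% with continuity correction. The stated 90% is not reproduced.

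**Could another convention give 90%?**

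| Variant, 20% vs 30% | Power |
|---|---|
| Stated design, pooled variance | 52.6% |
| Unpooled variance | 56.7% |
| Arcsine | 54.6% |
| Continuity-corrected (approximation) | 47.3% |
| Larger arm given to clonidine | 55.9% |
| One-sided 0.05 | 65.4% |
| 180 per arm, two-sided | 59.2% |
| 180 per arm, one-sided | 70.9% |
| 360 per arm, two-sided | 87.4% |
| 360 per arm, one-sided | 92.8% |

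Only the last two rows come near 90%, and both need 720 patients where the protocol states a total of 360. The one-sided rows also contradict section 14.4.

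**Sample size that would give 90%.** With 2:1 allocation,

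n_C = [1.96 × √(0.2667 × 0.7333 × 1.5) + 1.2816 × √(0.16 + 0.21/2)]² / 0.10² = (1.0615 + 0.6597)² / 0.01 = 296.3, rounded up to 297.

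This is 297 + 594 = **891** patients, about 2.5 times the planned number. For 80% power the same formula, with 0.8416 in place of 1.2816, gives 224 + 448 = 672.

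**What 240 and 120 patients can detect.** With clonidine at 20%, power is 80.1% for 34% on BUP/NX and 90.1% for 36.3%: differences of 14 and 16.3 points.

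**Precision at the assumed rates.** The half-width of the 95% confidence interval is 1.96 × 0.04699 = 0.092, or 9.2 points. An observed difference of exactly 10 points would only just exclude zero.

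**The case against.** The best defence rests on the word *maximally*. Section 14.6 attaches it to the 20% on clonidine and not to the 30% on BUP/NX, so 20% may be a ceiling. There are then two readings.

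- *BUP/NX stays at 30% and clonidine falls below 20%.* Power is 89.5% at 15% and 93.5% at 14%. This may be where the 90% came from, though the protocol does not say so. It also means that the stated rates are the least favourable case if 30% holds and 20% is a true upper bound. But these are gaps of 15 and 16 points, and section 14.6 ties its 90% to a gap of 10.
- *The 10-point gap is held and both rates fall.* Power is 59.0% for 15% vs 25%, 68.7% for 10% vs 20% and 83.5% for 5% vs 15%. It passes 90% only when clonidine is at about 3% (90.6% for 3% vs 13%), far from the stated 20%. So it would be wrong to say that no 10-point gap can ever reach 90%, but this does not help the stated case.

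Three further points are fair. The protocol gives no rule for interpreting a null result, so misreading one is a risk and not a certainty. Section 14.4 already provides for two-sided 95% confidence intervals in general, without naming the primary difference. And whether to enlarge the trial, revise the rates or accept lower power is for the sponsor to decide.

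None of this makes the printed figure correct. An analysis plan could not do so either, since this is a stated result on stated inputs and not a detail left open.

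**Conclusion.** The concern holds. On the protocol's own inputs, power is about 53% against the stated 90%, so the chance of missing a true 10-point benefit is about 47% and not 10%. No assumption from outside the protocol is needed. Every variant that keeps 20%, 30% and a total of 360 lies between about 47% and 71%.

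The error does not affect the type I error rate, and the trial is well powered if the true gap is about 16 points. It remains a plain error in the figure on which the size of the trial rests, and it must be corrected.

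**What to change.** Keep 360 patients and replace the power statement in section 14.6 with, for example:

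> With 240 BUP/NX and 120 clonidine patients, a chi-square test and a two-sided alpha of 0.05, power is about 53% for 20% vs 30% responders, 80% for 20% vs 34%, and 90% for 20% vs 36.3%.

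State there or in section 14.4 that the difference in responder proportions will be reported with its 95% confidence interval, and that a non-significant result will not be interpreted as absence of a 10-point effect.

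The cost is one paragraph of protocol wording and a less favourable stated power. Enrolment, allocation and the primary test do not change. If the sponsor needs 90% power for 20% vs 30%, the alternative is about 891 patients at 2:1. If it has grounds to expect a clonidine rate below 20% with BUP/NX still at 30%, section 14.6 should state that rate and the larger difference it implies. In any case the rates, the number of patients and the power must agree.

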14.7 Post Hoc Analyses

During the course of conducting the primary and other primary outcome analyses, the data may suggest other interesting differences in the treatment groups. Post hoc analyses are anticipated to explore these findings.

15.0 DATA MANAGEMENT AND CASE REPORT FORMS (CRF)

Data management activities and statistical analytical support will be coordinated by the Pacific Region Node and NIDA.

15.1 Data Collection

Data will be collected at the study sites on either electronic or paper CRFs. The Pacific Region Node will provide other participating nodes with a sample set of CRFs to incorporate in their data management system as appropriate. Each node will prepare identical and numbered CRFs with the data management system at use in the node. The CRFs will be distributed to the node's CTPs by the node data management center. These forms are to be completed on an ongoing basis during the study. The medical chart is the source of verification of data. Forms should be completed according to the instructions provided during training. The Investigator is responsible for maintaining accurate, complete and up-to-date records and for tracking receipt and return of CRFs for each patient. The Investigator is also responsible for maintaining any source documentation related to the study, including any films, tracings, computer discs or tapes.

Paper CRFs must be completed legibly with black ballpoint pen. A correction should be made by striking through the incorrect entry with a single line and entering the correct information adjacent to the incorrect entry. Corrections to paper CRFs must be initialed and dated by the person making the correction. Data entered into electronic CRFs shall be performed by authorized individuals. Corrections to electronic CRFs shall be tracked electronically with time, date, individual making the change, and what was changed. All CRFs should be reviewed by the investigator. Selected CRFs also require the investigator's written signature or electronic signature as appropriate.

During the study, the CRF will be monitored for completeness, accuracy, legibility and attention to detail. The investigator must retain a copy of all CRFs.

15.2 Data Accrual, Editing and Control

Completed forms/electronic data will be submitted on a regular basis to the node's data management center. When data are received at the node's data management center, it will be reviewed and if incomplete or inaccurate data are found a data clarification request will be forwarded to the sites for a response. Sites will resolve data inconsistencies and errors prior to returning data to the node's data management center. All corrections and changes to the data will be reviewed prior to being entered into the study database. Each node will be provided with instructions for the database physical and logical structures including the data dictionary to be developed within their data management system.

15.3 Data Entry, Processing and Analyses

Data will be entered into the database at each node using the data management system resident within each node. Periodically, during the investigation, data sets will be submitted to the NIDA DTR&D central data repository according to procedures provided during training. NIDA DTR&D central data repository will provide the completed database to the sponsor for data analysis.

15.4 Study Documentation and Records Retention

Study documentation includes all case report forms, data correction forms, electronic data files, workbooks, source documents, monitoring logs and appointment schedules, sponsor-investigator correspondence and regulatory documents (e.g., signed protocol and amendments, Ethics or Institutional Review Committee correspondence and approved consent form and signed patient consent forms, Statement of Investigator form, and clinical supplies receipt and distribution records).

Source documents include all recordings of observations or notations of clinical activities and all reports and records necessary for the evaluation and reconstruction of the clinical research study. Accordingly, source documents include, but are not limited to, laboratory reports, ECG tracings, X-rays, radiologist reports, patient/patient diaries, ultrasound photographs, patient/patient progress notes, hospital charts or pharmacy records and any other similar reports or records of any procedure performed in accordance with the protocol.

Whenever possible, the original recording of an observation should be retained as the source document; however, a photocopy is acceptable provided that it is a clear, legible, and exact duplication of the original document.

Government agency regulations and directives require that the investigator must retain all study documentation pertaining to the conduct of a clinical trial. These documents must

be kept for a minimum of two years after discontinuation of the IND or 2 years after the approval of an NDA.

16.2 Confidentiality of Patient Records

By signing the protocol the investigator agrees that within local regulatory restrictions and ethical considerations sponsor, sponsor's representative, NIDA or any regulatory agency may consult and/or copy study documents in order to verify case report form data.

APPENDIX I: TREATMENT SETTINGS

Pacific Region Node

Betty Ford Center: The Betty Ford Center at Eisenhower is a free-standing Chemical Dependency Recovery Hospital. It opened in October of 1982 on the campus of Eisenhower Medical Center in Rancho Mirage, California. Within the hospital there is an eighty (80) bed Residential Program, an Intensive Outpatient Program with a thirty (30) patient occupancy; and a Family educational component.

The interdisciplinary, medically managed, intensive residential program provides care on a twenty-four (24) hour per day basis, seven (7) days per week, for up to six weeks, depending on patient need. The intensive outpatient program operates five (5) days per week, for four to six (4-6) weeks, again depending on the needs of the patient. The family component is a five day educational program.

The Center accepts patients dependent on alcohol and/or other mood altering chemicals, and is open to all men and women eighteen (18) years of age or older, regardless of race, creed, sex, national origin, religion or sources of payment for care.

APPENDIX III: Proposed QA Monitoring Guidelines and Check List

On-site monitoring of clinical research is conducted to assess the progress of a trial and the accuracy of the data collected. It is the QA staffs' responsibility to monitor both the medical records for study participants and the CRFs for consistency, accuracy, and completeness for adherence to protocol requirements and FDA regulations and guidelines (21 CFR 312, subparts D & E).

The essential QA documents within the Regulatory Study Binder are denoted with an asterisk* Regulatory will monitor all other items within the study binders:

Regulatory Binder Sections:

*Protocol

Supplemental Protocol

*Consent Forms

*Case Report Forms

1572

Curriculum Vitae

Investigator Brochure

*Patient Log

*Serious Adverse Events

IRB Correspondence

Regulatory Documents

*Investigational Product Accountability

Lab Certification

DEA Certification

Signature Logs

*Visitor Log

Telephone Communications Log

Site-Sponsor Correspondence

*Patient Study Files

Other Correspondence

PROTOCOL

- Obtain copies of protocol (Regulatory Study binder) and look for correct version and IRB approval dates.
- Establish if enrolled participants meet the proper inclusion/exclusion criteria.
 - 1. Enrollment criterion:
 - a) Information provided on CRF forms Medical History Forms, Concomitant Medication Forms, Prior Medication Forms, Birth Control/Pregnancy Assessments, etc.
 - 2. Laboratory Information:
 - a) Results values within correct parameters for enrollment and continuation.
 - b) Time periods for testing correctly adhered to (e.g., urines).

CONSENT FORMS

- Look for correct version and IRB approval dates with IRB approval date-stamp.
- Ensure correct informed consent is located within the participant record.

CASE REPORT FORMS

• Indicate where they are located (at study site) in the Regulatory binder.

ADVERSE EVENTS

- These must be properly documented within the CRFs and individual patient charts and indicating the severity (AE or SAE) and also the adequacy of report dates.
- These must also be located in the Regulatory study binder (SAEs).

INVESTIGATIONAL PRODUCT ACCOUNTABILITY (STUDY MEDICATION)

- Study medication receipt forms Need to be completed and signed by investigator and staff.
- Security for controlled substances Where and how the medication is being stored.
- Study medication dispensing and return logs Ensure that investigational products are labeled and dispensed properly according to protocol.

PATIENT LOG

- Adequate documentation log of existence/participation of patients.
- Must be consistent with information (screening#, randomization# patient name code and consent date) within the CRFs and in the individual patient records.

VISITOR LOG

- Sign and date the log in this section to indicate and document the QA visit:
 - a) The date of the visit.
 - b) Name of the individual who conducted the visit.
 - c) A statement of the findings, conclusions and any actions taken to correct deficiencies noted during the visit.
 - d) Site director or study coordinator must sign log.

Please insert a QA monitoring/findings log within this section of the Regulatory Binder

Patient Study Files (Regulatory Binder must indicate where these are located at site)

- The following must be included:
 - a) Correct version of the approved informed consent
 - b) Medical history obtained This chart must have proper history to ascertain that the inclusion/exclusion criteria of the protocol are adhered to.
 - c) Copies of completed CRFs
 - d) SAE information

CHECK LIST

| PROTOCOL | P.I |
|-----------------|---------|
| SITE | AUDITOR |
| PATIENT I.D. NO | |

| PHASE | ITEM | YES | NO | NA | DATE |
|---------------|------------------------------------|-----|----|----|------|
| Screening | 1. Current version of signed | | | | |
| Bereeming | consent. | | | | |
| | 2. Signature, date & time prior to | | | | |
| | enrollment. | | | | |
| | 3. All pages initialed? | | | | |
| | 4. Copy of Informed Consent sent | | | | |
| | to Central Repository | | | | |
| Eligibility | 5. All pre-enrollment tests | | | | |
| Lingionity | documented. | | | | |
| | 6. Lab criteria met. | | | | |
| | 7. Inclusion criterion met. | | | | |
| | 8. Childbearing/lactating | | | | |
| | restrictions met. | | | | |
| | 9. Patient ruled out for exclusion | | | | |
| | criteria. | | | | |
| | 10. Waiver/exceptions | | | | |
| | documented. | | | | |
| | 11. Time Event Sheet completed. | | | | |
| Randomization | 12. Patient randomized according | | | | |
| | to protocol. | | | | |
| | 13. Time Event Sheet completed. | | | | |
| Medications | 14. Study med dispensed properly | | | | |
| | (time, duration, route, etc.) | | | | |
| | 15. Time-Event Sheet complete | | | | |
| | 16. Concomitant Meds | | | | |
| | documented. | | | | |
| | 17. Prescription/med orders in | | | | |
| | chart. | | | | |
| | 18. Any protocol-prohibited meds | | | | |
| | given. | | | | |
| | 19. Any protocol discrepancies | | | | |
| | reported to Site Coordinator, Site | | | | |
| | Director and/or Node PI. | | | | |
| AE Reporting | 20. Any SAEs | | | | |

| | 21 If yes, were they reported according to requirements (NIDA, | | |
|------------|--|--|--|
| | FDA, IRB, Etc.) | | |
| Assessment | 22. Was examination or instrument | | |
| Battery | administered according to | | |
| | schedule? Note any discrepancies. | | |
| | 23. Time Event Sheet completed. | | |
| | 24. Depending on how data is | | |
| | collected at each site, either QA | | |
| | will examine data forms on site or | | |
| | it will be done at Node's Data | | |
| | Management Center. | | |
| | 25. Missing, incomplete, or out-of- | | |
| | range value will be identified. The | | |
| | RA or Study Coordinator will be | | |
| | notified as soon as possible about | | |
| | potential errors. The RA or | | |
| | Coordinator will respond as soon as | | |
| | possible and resubmit corrected | | |
| | form. QA or DMC will verify that | | |
| | corrections have been made. | | |
| | 26. If consistent or systematic | | |
| | errors or an excessive numbers of | | |
| | errors are made on a given | | |
| | instrument, QA or DMC will notify | | |
| | Study Coordinator or Site Director. | | |
| Endpoints | 27. Missed visits documented and | | |
| | contact attempts noted. | | |
| | 28. If patient has reached any | | |
| | protocol defined endpoints, | | |
| | documentation and follow-up. | | |
| | 29. Time-Event Sheet complete. | | |

